### 4.2 Response Evaluable Set (RES)

The RES comprises all subjects in the FAS that at the timing of data cutoff date (for any interim reporting of the ongoing data).

- Measurable disease (see below),
- had  $\geq 1$  on-treatment disease assessment,
- have died within 60 days of first trial treatment without post-baseline disease assessment (these are included as non-responders)

Baseline measurable disease, based on laboratory data and/or scans, is defined as

#### ***RRMM***

- IgG, IgA, IgD, or IgM myeloma: Serum M-protein level  $\geq 0.5$  g/dL ( $\geq 5$  g/L) or urine M-protein level  $\geq 200$  mg/24 hours;  
***or***
- Light chain myeloma: Serum Ig free light chain (FLC)  $\geq 10$  mg/dL and abnormal serum Ig kappa lambda FLC ratio

#### ***DLBCL***

- A CT scan (or MRI) with involvement of  $\geq 2$  clearly-demarcated lesions/nodes with long axis  $> 1.5$  cm and short axis  $> 1.0$  cm;  
***or***
- 1 clearly-demarcated lesion/node with a long axis  $> 2.0$  cm and a short axis  $\geq 1.0$  cm

#### ***AML***

- bone marrow aspirate and/or biopsy blasts  $\geq 20\%$  at screening  
***or***
- for subjects who's response to last prior therapy was complete remission:
  - bone marrow aspirate and/or biopsy blasts  $\geq 5\%$ , or
  - reappearance of blasts in the blood, or

- development of extramedullary AML.

### **4.3 Safety Set**

See definition for FAS.

### **4.4 Per-Protocol Set**

Not applicable

### **4.5 Dose-Determining Analysis Set (DDS)**

The DDS will include all FAS subjects in the Dose Escalation part who meet the minimum exposure criterion and have sufficient safety evaluations or experience a DLT during the first 28 days of dosing (ie, in Cycle 1).

A subject will meet the minimum exposure criterion if the subject receives 4 out of the 4 preplanned doses during the DLT period. (The 2 initial split doses in Day 1 and Day 2 account for 1 preplanned dose.)

Per protocol: any DLTs observed in subjects in parallel cohorts will not directly contribute to the mBOIN design evaluation. Thus, to clarify, subjects in parallel cohorts are not included in the DDS.

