#### **4.1.2.4 *Parallel DL(s) for Clinical Confirmation***

To better understand the safety, tolerability, PK, pharmacodynamics, or anti-tumor activity, up to 7 additional subjects may be allocated in parallel to DLs that are considered safe for such allocation (DLs at or below the currently investigated one).

Any DLTs observed in such subjects will not directly contribute to the mBOIN design evaluation. However, if the mBOIN algorithm later stipulates de-escalation to an over-recruited DL, all subjects on that dose will be included in the mBOIN algorithm.

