## **9.3 Populations for Analyses**

**Full Analysis Set (FAS):** The FAS and safety set are defined in the same way and will comprise all enrolled subjects who receive at least 1 dose of trial drug (GEN3014 or daratumumab SC). In case of any deviations from planned dosing, subjects will be treated as per actual dosing.

The FAS will be used to summarize efficacy and safety analyses.

**Response Evaluable Set (RES):** Comprises all subjects in the FAS that at the timing of data cutoff date (for any interim reporting of the ongoing data):

- have measurable disease at baseline;
- had  $\geq 1$  on-treatment disease assessment;
- have died within 60 days of first trial treatment without post-baseline disease assessment (these are included as non-responders)

**Safety Set:** See definition for FAS.

**Per-Protocol Set:** Not applicable

**Dose-Determining Analysis Set (DDS):** The DDS will include all FAS subjects in the Dose Escalation part who meet the minimum exposure criterion and have sufficient safety evaluations or experience a DLT during the first 28 days of dosing (ie, in Cycle 1).

A subject will meet the minimum exposure criterion if the subject receives 4 out of the 4 preplanned doses during the DLT period. (The 2 initial split doses in Day 1 and Day 2 account for 1 preplanned dose.)

**Pharmacokinetic Analysis Set 1 (PAS1):** The PAS1 will include all enrolled subjects who receive at least 1 dose of trial drug (GEN3014 or daratumumab SC) and who provide at least 1 evaluable PK sample.

**Pharmacokinetic Analysis Set 2 (PAS2):** The PAS2 will include all enrolled subjects who received all 8 weekly GEN3014 or daratumumab SC doses in Cycles 1 and 2 with the cumulative dose administered amounting to 80% to 125% of the planned dose and provided a predose PK blood sample on Cycle 3 Day 1.

**Immunogenicity Analysis Set (IAS):** The IAS will include all enrolled subjects who receive at least 1 dose of trial drug (GEN3014 or daratumumab SC) and have a baseline and at least 1 evaluable on-treatment ADA sample.

**Biomarker Analysis Set (BAS):** The BAS will include all enrolled subjects who receive at least 1 dose of trial drug (GEN3014 or daratumumab SC) and have at least 1 evaluable biomarker sample.

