## 5.3 Primary Endpoint(s) Analysis

### **Dose Escalation**

The primary endpoints in the Dose Escalation phase are the DLTs (presented based on the DDS), general AEs and safety laboratory parameters (presented based on the FAS/SAF). Safety analyses are described in Section 5.5.

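### The SAP removes all parallel (backfill) subjects from the dose-determining set, an exclusion the supplied protocol does not make, so their DLTs drop out of the reported primary DLT incidence

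*SAP*

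**What the plan says.** Four places bear on this.

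- **Protocol 9.3** defines the set: "The DDS will include all FAS subjects in the Dose Escalation part who meet the minimum exposure criterion and have sufficient safety evaluations", or who have a DLT in Cycle 1. Parallel subjects are not excepted.
- **Protocol 4.1.2.4** allows extra subjects at levels already judged acceptable: "up to 7 additional subjects may be allocated in parallel to DLs that are considered safe for such allocation". It then says: "Any DLTs observed in such subjects will not directly contribute to the mBOIN design evaluation". The next sentence qualifies this: "However, if the mBOIN algorithm later stipulates de-escalation to an over-recruited DL, all subjects on that dose will be included in the mBOIN algorithm".
- **SAP 4.5** opens with the same general definition as protocol 9.3. It then cites the protocol for the rule on mBOIN input, stops before the qualifying sentence, and concludes: "Thus, to clarify, subjects in parallel cohorts are not included in the DDS".
- **SAP 5.3 (Dose Escalation)** fixes the population for the primary endpoint: "The primary endpoints in the Dose Escalation phase are the DLTs (presented based on the DDS", with general AEs and safety laboratory data placed on the FAS.

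Incidence of DLTs is a primary endpoint of Dose Escalation in both documents (protocol Table 3-1, SAP Table 1). SAP 6.1, which should record departures from protocol-planned analyses, says not applicable.

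**The concern.** The SAP turns a rule about what feeds the escalation algorithm into a rule about who counts in the reported primary endpoint. The two need not coincide. Parallel subjects are enrolled to learn more about a dose, including its safety and tolerability, yet they are left out of the set on which DLT incidence is presented.

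The exclusion also fails if the DDS was meant to mirror mBOIN. After de-escalation to an over-recruited level, every subject on that level enters the algorithm. Under SAP 4.5 the parallel subjects among them would have helped to determine the dose and would still be absent from the dose-determining set.

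At stake is the agreement of a primary endpoint's population with the protocol, in a place where the SAP declares no departure.

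**Working it through.** **1. The plan's own figures.** Protocol 4.1.2 states mBOIN boundaries of 24% and 36% for a target φ = 0.30, with φ1 = 0.6φ = 0.18 and φ2 = 1.4φ = 0.42.

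- Escalation: ln[(1−φ1)/(1−φ)] / ln[φ(1−φ1)/(φ1(1−φ))] = ln(0.82/0.70) / ln(0.246/0.126) = 0.2365.
- De-escalation: ln[(1−φ)/(1−φ2)] / ln[φ2(1−φ)/(φ(1−φ2))] = ln(0.70/0.58) / ln(0.294/0.174) = 0.3585.

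Both agree with the protocol. The caps also agree: 9 × 6 = 54 for RRMM and 6 × 3 = 18 for AML. The algorithm's numbers are therefore sound; the problem is the analysis set.

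**2. The texts side by side.**

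| Question | Protocol | SAP 4.5 |
|---|---|---|
| Are parallel subjects in the DDS? | Yes, if they qualify (9.3) | Never |
| Do their DLTs directly drive mBOIN? | No (4.1.2.4) | No |
| After de-escalation to an over-recruited level? | All subjects on that dose enter mBOIN (4.1.2.4) | Not mentioned |

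Only the second row agrees, and it is the row the SAP cites.

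**3. Effect on the denominator.** Let m be the mBOIN subjects at a level and k the DLT-evaluable parallel subjects there. The SAP set has m subjects, the protocol set has m + k, and the share omitted is k/(m + k). The protocol gives up to 7 parallel subjects but does not say whether that is per level or overall, and evaluability is not guaranteed. I therefore show k = 7 (all at one level, all evaluable) and, as an assumed smaller case, k = 3.

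| m | k = 7: SAP vs protocol | Omitted | k = 3: SAP vs protocol | Omitted |
|---|---|---|---|---|
| 3 (level cleared on one cohort) | 3 vs 10 | 70% | 3 vs 6 | 50% |
| 6 (AML cap) | 6 vs 13 | 54% | 6 vs 9 | 33% |
| 9 (RRMM cap) | 9 vs 16 | 44% | 9 vs 12 | 25% |

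**4. Chance that at least one DLT is omitted:** 1 − (1 − p)^k, where the true DLT rate p is an assumption.

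| p | k = 7 | k = 3 |
|---|---|---|
| 5% | 1 − 0.95^7 = 30% | 1 − 0.95^3 = 14% |
| 10% | 1 − 0.90^7 = 52% | 1 − 0.90^3 = 27% |
| 20% | 1 − 0.80^7 = 79% | 1 − 0.80^3 = 49% |

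**5. Direction.** The effect can go either way. No DLT in 3 mBOIN subjects and one in 7 parallel subjects reads 0/3 = 0% under the SAP and 1/10 = 10% under the protocol. One DLT in 6 mBOIN subjects and none in 7 parallel subjects reads 1/6 = 16.7% against 1/13 = 7.7%.

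**The case against.** The strongest reply is that little depends on this table. Protocol 4.1.2.5 bases the RP2D on a review of all accumulated data, including AEs and observations after the DLT period, and the Dose Escalation Committee sees everything available. Protocol 4.3.2 already reports 16 mg/kg as selected. Parallel subjects remain in the FAS and safety set, so their toxicities appear in the TEAE tables and the listings. The part is descriptive, with no hypothesis test. All of this stands, and it limits the consequence to the reported endpoint. A reader might infer that the exclusion hides toxicity or distorts the dose choice; the documents do not support that.

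Two other stronger readings also go too far.

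- **Two conflicting DLT incidences.** SAP 5.5.2.2 lists a DLT tabulation without naming an analysis set. It could follow the DDS, as SAP 5.3 implies, or the FAS, which SAP 4.1 names for safety summaries. Conflict is possible but not established.
- **A needlessly wide confidence interval.** With no DLTs the exact 95% upper limit is 1 − 0.025^(1/n), which is 70.8% for 0/3 and 30.8% for 0/10. Neither document plans an interval for DLT incidence, so this contrast does not describe a planned output.

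It is also fair to say that the SAP was written to protocol Amendment 3, while the supplied protocol is Amendment 5. The Amendment 5 list of changes names neither 9.3 nor 4.1.2.4, but the Amendment 3 text is not available, so the mismatch is shown only against the current protocol. The SAP does, however, carry the same general DDS sentence and then contradicts it. Finally, pooling is not the only remedy: an openly declared algorithm-only set could also be defended.

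**Conclusion.** The point holds. SAP 4.5 excludes every parallel subject from the DDS on the authority of a protocol rule that limits only direct input to mBOIN, and it leaves out the re-entry exception attached to that rule. The result disagrees with protocol 9.3 and with the SAP's own opening sentence, and SAP 6.1 does not declare it. DLT-evaluable parallel subjects and their DLTs are therefore missing from the reported primary DLT incidence, including any who entered the algorithm after de-escalation.

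The size depends on how parallel subjects were allocated, which the documents do not give. The 3 vs 10 and 9 vs 16 denominators, and the 30%, 52% and 79% chances, assume that all 7 are evaluable at one level and that true DLT rates are 5%, 10% and 20%. With fewer evaluable subjects at a level the effect is smaller. If 7 is a per-level figure, the total omitted across levels could exceed 7. The harm is to the reported primary endpoint; no effect on the dose decision is shown.

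**What to change.** 1. In SAP 4.5, delete the sentence that excludes parallel cohorts, so that the DDS matches protocol 9.3.
2. Define a separately named mBOIN-evaluable subset that follows protocol 4.1.2.4 in full, including re-entry of all subjects on a level after de-escalation to it.
3. Report DLT incidence by dose level on the full DDS, with the mBOIN subset beside it. Exact confidence intervals are optional.
4. Name the same analysis set for the DLT tabulation in SAP 5.5.2.2.

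If the sponsor prefers to keep the exclusion, it should be declared and justified in SAP 6.1, the re-entry exception added, and DLTs in parallel subjects shown by dose level alongside the primary table.

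Either route costs SAP wording and one extra table column. No new data are needed.

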### **4.6 Pharmacokinetic Analysis Set 1 (PAS1)**

The PAS1 will include all enrolled subjects who receive at least 1 dose of trial drug (GEN3014 or daratumumab SC) and who provide at least 1 evaluable PK sample.

### **4.7 Pharmacokinetic Analysis Set 2 (PAS2)**

The PAS2 will include all enrolled subjects who received all 8 weekly GEN3014 or daratumumab SC doses in Cycles 1 and 2 with the cumulative dose administered amounting to 80% to 125% of the planned dose and provided a predose PK blood sample on Cycle 3 Day 1.

### **4.8 Immunogenicity Analysis Set (IAS)**

The IAS will include all enrolled subjects who receive at least 1 dose of trial drug (GEN3014 or daratumumab SC) and have a baseline and at least 1 evaluable on-treatment ADA sample.

### **4.9 Biomarker Analysis Set (BAS)**

The BAS will include all enrolled subjects who receive at least 1 dose of trial drug (GEN3014 or daratumumab SC) and have at least 1 evaluable biomarker sample.

## 5 STATISTICAL ANALYSES

### 5.1 General Considerations

Analyses will be carried out using SAS (Version 9.4 or higher), unless otherwise noted.

In general, continuous variables will be summarized using descriptive statistics such as mean, standard deviation (Std Dev), median, minimum, and maximum. Categorical variables will be summarized using absolute count and percentage (relative to analysis set).

Estimates of time to event variables will be provided based on Kaplan-Meier (KM) methods with the number and percentage of subjects with event or censoring reported. 95% CI of the KM estimate will be provided using the log-log transformation. Median times with 95% CI (based on the Brookmeyer and Crowley method) will be reported. Landmark event-free rates with 95% confidence intervals may also be presented.

#### 5.1.1 *Trial Days, Cycle Days and Treatment Periods*

##### 5.1.1.1 *Trial Days*

Trial Day 1 or Day 1 refers to the day of first drug administration. Trial day or relative day for a visit is defined as:

- Visit date - date of Day 1, if visit date < date of Day 1
- Visit date - (date of Day 1) +1, if visit date is  $\geq$  date of Day 1

There is no 'Day 0'.

##### 5.1.1.2 *Treatment Periods*

The treatment periods are three mutually exclusive segments:

- The pre-treatment period includes information collected from the date of informed consent until the day prior to the first dose of trial treatment (subjects not receiving trial medication will remain in the pre-treatment period for the remainder of their trial participation). Any information collected on the day of first dose where timepoint is also collected will be assigned to the pre-treatment period if occurring prior to time of first dose
- The on-treatment period begins on the date of the first dose of trial treatment (refer to bullet above for exception) and lasts up until date of safety-follow up visit, the date of start of subsequent anti-cancer therapy, date of trial discontinuation, date of loss to follow-up, date of administrative cut-off, or date of death, whichever occurs first

- Note: Any information collected on the day of start of subsequent anti-cancer therapy, where timepoint is also collected, will be assigned to the post-treatment period if occurring after time of first dose of subsequent anti-cancer therapy
- The post-treatment period begins at end of the on-treatment period + 1 day

If incomplete data makes it impossible to definitively assign an observation to one of these periods, the data will be conservatively assigned to the on-treatment period.

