- Subjects discontinuing from treatment for any reason will have a safety follow-up visit 30 days (+7 days) after the last dose of GEN3014 or daratumumab. If the subject initiates new anti-cancer therapy within 60 days of the last dose of GEN3014 or daratumumab, the safety follow-up visit should be performed prior to starting new anti-cancer therapy. Once new anti-cancer treatment is initiated, the subject will move into survival status follow-up.
- Subjects will enter the survival follow-up after completion of the safety follow-up or if new anti-cancer treatment has been started. Survival follow-up contact may be performed as a telephone call, email, or on-site visit.
- Baseline is defined as the available data from the latest recorded measurement made before the first GEN3014 or daratumumab administration.
- Any medical condition (signs, symptoms, and diagnosis) or procedures occurring prior to first GEN3014 or daratumumab dose should be documented as medical history. Medical conditions that occur after the ICF is signed and prior to first GEN3014 or daratumumab dose should only be reported as AEs if they were assessed by the investigator to be caused by a protocol-mandated procedure (ie, tumor biopsy and/or CT scan), including washout or discontinuation of prior medications.
- Only SAEs judged by the investigator as related to GEN3014 or daratumumab should be reported after the safety follow-up period.
- During Cycle 1, subject must be observed after each GEN3014 infusion or daratumumab injection for 4 hours. Additional or longer monitoring is permissible per the investigator's discretion. If a subject has an IRR or sARR of ≥ grade 3 during any infusion or injection, the subject will be required to stay overnight in hospital.
- During Cycle 1, the first dose of GEN3014 (16 mg/kg) is split into 2 consecutive days, ie, C1D1 (8 mg/kg) and C1D2 (8 mg/kg). For all subsequent dosing visits, full dose of GEN3014 is administered on C1D8, C1D15, and C1D22.

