#### **7.1.1 Safety Follow-up Evaluation**

Subjects discontinuing from treatment for any reason will have a safety follow-up visit 30 days ( $\pm 7$  days) after the subject receives the last dose of GEN3014 or daratumumab SC. If the subject initiates new anti-cancer treatment within 30 days of the last dose of GEN3014 or daratumumab SC, the safety follow-up visit should be performed prior to starting new anti-

cancer treatment. Once new anti-cancer treatment is initiated, the subject will move into survival status follow-up (see Section 7.1.2).

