#### **8.4.2 Adverse Event Reporting**

All AEs, whether serious or non-serious (see definitions in Section 10.3), will be documented from the first dose of GEN3014 or daratumumab SC until 30 days after the last dose of GEN3014 or daratumumab SC, subject withdrew consent, subject started new anti-cancer treatment, or the subject died, whichever comes first, as documented in the Schedule of Activities, Section 1.3.

As noted in Section 8.1.3, medical conditions (signs, symptoms, and diagnosis) that occur after the ICF is signed and prior to the first dose should only be reported as AEs if they were assessed by the investigator to be caused by a protocol-mandated procedure (ie, tumor biopsy and/or CT scan).

For details regarding follow-up of AEs and SAEs, see Section 8.4.6, Follow-up of Adverse Events and Serious Adverse Events.

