## 5.5.2 *Adverse Events*

### 5.5.2.1 *Definition Treatment Emergent Adverse Event*

A treatment emergent adverse event (TEAE) is defined as any AE with an onset date or worsening grade (relative to the last reported grade before the on-treatment period) within the on-treatment period, defined in Section 5.1.1.2.

A pre-treatment AE is defined as any non-treatment emergent AE with onset during the pre-treatment period, with no worsening during the on-treatment period.

Only SAEs judged by the investigator as related to GEN3014 should be reported during the post-treatment period.

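### The SAP ends the TEAE period at the safety follow-up visit rather than a fixed number of days after last dose, so an early visit leaves collected AEs outside the TEAE tables and a missed visit leaves the period without a day limit

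*SAP*

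**What the plan says.** SAP 5.1.1.2 closes the on-treatment period at the earliest of six events. It "lasts up until date of safety-follow up visit, the date of start of subsequent anti-cancer therapy, date of trial discontinuation", with loss to follow-up, administrative cut-off and death completing the list. No term counts days from the last dose. The next period follows directly: "The post-treatment period begins at end of the on-treatment period + 1 day".

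SAP 5.5.2.1 rests the TEAE definition on this: "A treatment emergent adverse event (TEAE) is defined as any AE with an onset date or worsening grade", relative to the last grade before treatment, "within the on-treatment period, defined in Section 5.1.1.2". The serious, Grade 3 or higher, related and fatal TEAE tables in SAP 5.5.2.2 inherit the window, as do the worst on-treatment laboratory summaries in SAP 5.5.4.1.

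Protocol 8.4.2 documents all AEs from first dose "until 30 days after the last dose of GEN3014 or daratumumab SC, subject withdrew consent, subject started new anti-cancer treatment, or the subject died"; the earliest of these applies. Protocol 8.4.6 limits reporting after the safety follow-up period to related SAEs.

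The protocol gives the visit two windows. Section 7.1.1 states "Subjects discontinuing from treatment for any reason will have a safety follow-up visit 30 days", plus or minus 7 days, after the last dose. The schedules allow lateness only; Table 1-12, for example, has a "safety follow-up visit 30 days (+7 days) after the last dose of GEN3014 or daratumumab". Both places also bring the visit forward when new anti-cancer therapy is about to start, within 30 days of last dose in 7.1.1 and within 60 days in Table 1-12.

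**The concern.** A TEAE window should be the same function of exposure for every subject. Here its end depends on when, and whether, one visit takes place. Two consequences follow.

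- **Visit before day 30.** An AE that starts after the visit but within the 30 days is collected under the protocol, yet the SAP classes it as post-treatment. It drops out of every TEAE table. SAP 5.5.2.1 adds to the confusion by stating that only SAEs related to GEN3014 should be reported in the post-treatment period, whereas protocol 8.4.2 still requires every AE up to day 30.
- **Visit missed.** If no new therapy, discontinuation, loss to follow-up, death or cut-off intervenes, the subject stays on treatment for analysis purposes. A related SAE months later is a TEAE for that subject. The same event in a subject who attended is not.

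AE incidence and severity is a primary endpoint in Dose Escalation and a secondary endpoint in both expansion parts. Part B compares two arms, so a common window matters there in particular.

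**Working it through.** There is no planned figure to reproduce. The check is day arithmetic, counting days after the last dose.

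**Inputs**
- AE collection ends at day 30, or at new therapy if earlier (protocol 8.4.2).
- The on-treatment period ends at the visit, or at new therapy if earlier (SAP 5.1.1.2).
- The visit falls on days 23 to 37 under protocol 7.1.1 (30 − 7 and 30 + 7), or days 30 to 37 under the schedules.

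**Formulas**
- Collection end C = min(30, therapy day)
- SAP end S = min(visit day, therapy day)
- Collected days outside the TEAE period = max(0, C − S)
- Days the TEAE period runs past collection = max(0, S − C)

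**Attended visit, no early new therapy**

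| Visit day | Collected days lost | Days past collection |
|---|---|---|
| 23 | 7 | 0 |
| 26 | 4 | 0 |
| 29 | 1 | 0 |
| 30 | 0 | 0 |
| 37 | 0 | 7 |

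The largest loss is 7/30 = 23% of the post-dose collection window. If visits were spread evenly over days 23 to 37 (an assumption; the documents give no distribution), 7 of 15 visit days (47%) would lose something. The mean loss would be (7+6+5+4+3+2+1)/15 = 28/15 = 1.9 days. Under the schedules' window the loss is 0 for every visit day.

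**Visit brought forward for new therapy (illustrative dates)**
- Visit day 14, therapy day 28: C = 28, S = 14, so 14 days are lost.
- Visit day 7, therapy day 29: C = 29, S = 7, so 22 days are lost.

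This route is open under either visit window.

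**Visit missed, no other terminating event (illustrative follow-up)**
- 3 months × 30.4375 = 91 days
- 6 months × 30.4375 = 183 days
- 17 months × 30.4375 = 517 days

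Each compares with 30 days. Seventeen months is the protocol's estimated post-treatment follow-up in RRMM (protocol 4.4.1). These are window lengths, not event counts.

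**After the fix.** With the SAP end at min(30, therapy day, other terminating events), no collected day is lost whatever the visit date, and a subject who misses the visit stops at day 30.

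**The case against.** The strongest reply is that the protocol's TEAE definition is not contradicted. Collecting AEs "until 30 days after the last dose of GEN3014 or daratumumab SC" is a collection rule, and protocol 9.4.5.1 builds its tables on the on-treatment period without giving it a length in days. That stands: this is a misalignment between two windows, not a breach of a stated definition.

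Second, every schedule table allows only a late visit, and a visit on days 30 to 37 loses nothing. That also stands, and it makes the loss conditional. It does not remove the loss, because 7.1.1 permits an earlier visit and both places bring the visit forward for new therapy. The SAP cites protocol version 5.0 and the protocol at hand is version 8.0. The Amendment 5 change list for 7.1.1 mentions only the addition of daratumumab SC, so the documents do not show when the two visit windows diverged.

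Third, a reader might infer that fatal AEs disappear. They do not. SAP 5.5.3 lists every fatal AE, summarizes all deaths by primary cause, and tabulates deaths in the 30 and 60 days after the first and the last GEN3014 dose. An event that is already a TEAE and later reaches Grade 5 stays in the TEAE tables (SAP 5.5.2.2), and all AEs are listed with period flags. What remains is narrower: a fatal AE with onset after an early visit is absent from the fatal TEAE table. The 30- and 60-day death tables name GEN3014 only, so daratumumab subjects have just the all-deaths table and the listings.

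Fourth, a reader might take 517 days against 30 as a seventeen-fold excess of events. After day 30 only related SAEs are reported (protocol 8.4.6), so the open end mainly adds late related SAEs.

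Fifth, a loss of laboratory data might be inferred. After End of Treatment the only scheduled hematology and biochemistry is at the safety follow-up visit itself, where local authorities require it. None is scheduled between an early visit and day 30.

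Finally, bias through illness is not shown. The documents contain nothing on visit attendance by health status, and a subject too ill to attend who then dies remains on treatment until death, so that event is kept.

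**Conclusion.** The point holds as a conditional misalignment that is cheap to remove. When the visit precedes day 30, up to 7 of the 30 collected days fall outside the TEAE period under the 7.1.1 window. More can fall outside when the visit is brought forward: 14 and 22 days in the two illustrations. When the visit is missed and nothing else intervenes, the period has no day limit and late related SAEs are counted unevenly across subjects.

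How many events this would move cannot be estimated, because the documents give no visit-timing or attendance figures. They do not support saying that AEs or deaths will routinely be lost, or that the SAP overrides a protocol TEAE definition. SAP Appendix 1 records no change from the planned analyses, so nothing in the plan explains why a visit date was chosen over a day count.

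**What to change.** In SAP 5.1.1.2, replace the safety follow-up visit as a terminating event with the date of last trial drug administration + 30 days. Keep the other terminating events, whichever occurs first. State that safety laboratory values drawn at a safety follow-up visit on days 31 to 37 still count in the on-treatment laboratory summaries; otherwise the new end date would exclude values from a visit that complied with the schedule.

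The protocol's visit windows, plus or minus 7 days in 7.1.1 and +7 days in the schedules, contradict each other and must be reconciled. So must the 30-day and 60-day clauses for bringing the visit forward. The SAP change works however they are settled.

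The cost is one changed line and one added sentence in the SAP. No new data are needed, since dosing dates and AE onset dates are already recorded. The small downside is that related SAEs with onset on days 31 to 37 move from the TEAE tables to the post-treatment listing.
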